4.2. Exclusion Criteria

Patients who meet any of the following criteria in screening tests and observations within 28 days before enrollment will be excluded from the study.

- 1) Another previous or current malignancy, with the following exceptions:
 - a) Curatively treated intraepithelial cervical cancer, basal cell carcinoma, superficial bladder cancer (Ta, Tis, or T1), early gastric cancer, or other early cancers with low risk of recurrence after curative therapy
 - b) Disease-free for more for than 3 years after curative therapy at the time of enrollment
- 2) Renal failure requiring hemodialysis or peritoneal dialysis
- 3) Any of the following heart diseases:
 - a) Congestive heart failure classified as NYHA (appendix 1) class III or IV
 - b) Active coronary artery disease or ischemic heart disease such as cardiac infarction within 6 months prior to screening
 - c) Serious cardiac arrhythmia (\geq grade 3 according to the Japanese translation of CTCAE v4.0: arrhythmia for which nonsurgical emergency treatment is indicated)
- 4) Poorly controlled hypertension
- 5) Active clinically serious infections (\geq grade 3 according to the Japanese translation of CTCAE v4.0) other than HBV and HCV
- 6) Active chicken pox
- 7) Hearing impairment
- 8) History of HIV infection
- 9) Known meningeal tumor (including meningeal metastasis)
- 10) Extensive extrahepatic tumor spread (except that which does not affect the prognosis)
- 11) History of seizure disorder requiring treatment (may have a seizure)
- 12) Clinically significant gastrointestinal bleeding within 4 weeks prior to study enrollment
- 13) Thrombosis or embolization (e.g., transient ischemic disease, deep vein thrombosis, or pulmonary embolization) within 6 months prior to study enrollment, except portal vein thrombosis
- 14) Any history of the following treatments:
 - a) Currently using a CYP3A4 inhibitor (e.g., rifampicin)
 - b) Invasive surgical procedure (e.g., thoracotomy or laparotomy) within 4 weeks

prior to starting the study treatment

c) History of organ allograft

- 15) Unable to swallow oral medications
- 16) Gastrointestinal disease that may affect drug absorption or pharmacokinetics
- 17) Using medication that may affect drug absorption or pharmacokinetics
- 18) Disease or disorder that may affect metabolism, and thus evaluation of the study drugs
- 19) Enrolled in another clinical study within 4 weeks prior to study enrollment
- 20) Currently pregnant, may be pregnant, plans to become pregnant, or is breastfeeding
- 21) Allergy to any of the study drugs
- 22) Substance abuse or a medical, psychological, or social condition that is likely to interfere with the patient's participation in the study or in terms of evaluation of study results, in the investigator's judgment
- 23) Any other condition that is unstable or could jeopardize the safety of the patient or their compliance with the protocol, in the investigator's judgment

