4.1. Inclusion Criteria

Patients who meet all of the following criteria in screening tests and observations within 28 days before enrollment will be included in the study.

- 1) At least 20 years of age (male or female)
- 2) Life expectancy of at least 12 weeks
- 3) Advanced hepatocellular carcinoma diagnosed as typical hepatocellular carcinoma histologically, cytologically, or by diagnostic imaging such as dynamic CT (MDCT), dynamic MRI, or CTHA/CTAP

*Patients who meet any of the following criteria are considered to have advanced hepatocellular carcinoma.

- (1) Multiple hepatocellular carcinoma with at least 4 tumors
 - (2) Hepatocellular carcinoma with vascular invasion
 - (3) Hepatocellular carcinoma with extrahepatic spread that does not affect the prognosis
- 4) Not a candidate for complete resection by hepatectomy, local ablation therapy, or transcatheter arterial chemoembolization, or is unlikely to respond to those treatments
 - 5) ECOG performance status (PS) of 0 or 1
 - 6) Child-Pugh score of 7 or lower (PT calculated as INR)
 - 7) Laboratory test values are within the prescribed ranges below. Patients can be re-tested during the screening period within 28 days before enrollment.
 - a) Hemoglobin \geq 8.5 g/dL
 - b) Neutrophil count \geq 1,500/ μ L
 - c) Platelet count \geq 50,000/ μ L
 - d) PT-INR \leq 2.3
 - e) Total bilirubin \leq 2 mg/dL
 - f) ALT and AST \leq 6 times the institutional upper limit of normal
 - g) Serum creatinine \leq 1.5 times the institutional upper limit of normal
 - h) Amylase \leq 2 times the institutional upper limit of normal

- 8) Provided written informed consent to participate in the study

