6. TREATMENT PLANS AND CRITERIA FOR ADJUSTING TREATMENT

6.1. Protocol Treatments

6.1.1. Low-dose FP and sorafenib group (combination therapy group) (Table 1)

This study will use the following doses demonstrated as safe in a phase I/II study of sorafenib and low-dose cisplatin/fluorouracil hepatic arterial infusion chemotherapy for advanced hepatocellular carcinoma. Cisplatin will be administered at a dose of 20 mg/m² on day 1 (within 30 days), and fluorouracil will be administered at a dose of 330 mg/m²/day by hepatic infusion using a reservoir for 5 days from day 1 through day 5 (continuous infusion over 24 h), followed by 2 days off. This sequence will be repeated for 2 weeks, followed by 2 weeks off. Sorafenib will be administered continuously at a dose of 400 mg twice daily for 28 days from day 1 to day 28. This 4-week period constitutes one cycle.

The first cycle of treatment will be started within 28 days of randomization. Treatment with sorafenib before hepatic arterial infusion chemotherapy will be allowed. However, patients must be off sorafenib for 2 days before and 7 days after reservoir placement. The next cycle of treatment will be started within 14 days. Sorafenib will be continued until the start of the next cycle. This combination therapy will be continued until discontinuation of the protocol treatment.

If an adverse event is observed, treatment will be interrupted or the dose will be reduced as appropriate in accordance with **6.3.2. Criteria for adjusting the sorafenib dose (dose interruption and reduction)** and **Section 6.3.3. Criteria for Hepatic Arterial Infusion Chemotherapy (Low-dose FP) Dose Adjustment (Dose Interruption and Reduction)**. After the protocol treatment is discontinued, appropriate treatment as described in **Section 6.5 Post-trial Treatment** will be instituted.

The arterial catheter should be placed in a manner that allows for proper drug distribution throughout the liver, and the flow should always be checked by contrast CT through the port or by DSA before starting treatment.

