6.2. Criteria for Discontinuation of the Protocol Treatment

In general, in situations such as the following, the protocol treatment will be discontinued, a note to that effect will promptly be written on the patient’s medical records, and a Treatment Completion Report will be faxed to the data center.*

- 1) Progressive disease
 - a) Progressive disease (PD) as defined by the modified RECIST criteria is confirmed by imaging**
 - b) Worsening of general condition indicates a lack of clinical response to treatment
- 2) Patient cannot continue the study due to an adverse event
 - a) Patient cannot resume sorafenib after 8 weeks of interruption due to an

adverse event

b) Patient cannot start the next cycle of treatment within 8 weeks after completing the previous cycle due to an adverse event

c) An adverse event that meets the criteria for dose reduction occurs after the dose was already reduced to the lowest level

(Reducing the dose to below the lowest level in the dose reduction criteria stipulated in the protocol will be considered discontinuation of the protocol treatment, and all treatment after that point will be considered post-trial treatment.)

3) Hepatic arterial infusion chemotherapy becomes technically infeasible

4) Patient requests to discontinue the study

5) Patient can no longer make continuous visits due to moving or changing doctors

6) Death

7) An investigator determines that discontinuation is necessary for any other reason

8) The patient shows a CR

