7.2. Adverse Events Caused by Catheters and Reservoirs

Events such as bleeding associated with arterial puncture, hematoma, intimal injury, neuropathy, aneurysm, arteriovenous fistula, infection, pain (all rare), blood vessel perforation by the catheter/guidewire (rare), spasms and obstruction (rare), infection and pain (rare), nausea/vomiting (20%), vagal response (rare), shock caused by iodine contrast medium (very rare), and foreign matter left in blood vessels after equipment breakage (very rare) are anticipated to occur during catheterization before the start of the study. These events may also occur later. Events such as hemorrhage, hematoma, intimal injury, neuropathy, infection, and pain are also anticipated with reservoir placement.

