8.1. Parameters Assessed Before Enrollment

Data on the following parameters will be collected within 4 weeks before enrollment for pre-enrollment evaluation.

- 1) Patient characteristics: Sex, height, pathological diagnosis, treatment history, disease stage (using the General Rules for the Clinical and Pathological Study of Primary Liver Cancer, see Section 21.3), ECOG-PS (see Section 21.2), allergies, and concomitant diseases
- 2) Signs and symptoms and blood pressure
- 3) Body weight
- 4) Chest X-ray
- 5) Electrocardiogram
- 6) Target lesion measurements (dynamic CT is preferred, but dynamic MRI is also acceptable)
- 7) Hematology parameters: Hemoglobin, white blood cell count, neutrophil count, red blood cell count, platelet count
- 8) Blood biochemistry: AST, ALT, total bilirubin, direct bilirubin, ALP, γ -GTP, albumin, creatinine, Na, K, Cl, amylase, lipase, blood glucose
- 9) Coagulation: PT (INR)
- 10) Tumor markers: AFP, AFP-L3 fraction, PIVKA-II
- 11) Hepatitis virus: HBs antigen/HBs antibody/Hbc antibody,*¹ HCV antibody*²

*1 If the patient tests positive for Hbs antibody and/or Hbc antibody, HBV DNA will be analyzed following the methods in the “Guidelines for Management of Hepatitis B Virus Caused by Immunosuppressive Therapy and Chemotherapy” [28] (see **21.5 Guidelines for Management of Hepatitis B Virus Caused by Immunosuppressive Therapy and Chemotherapy**).[[not a link]] Patients who test positive for HBV DNA will be provided appropriate treatment.

*2 Patients who test positive will be tested for HCV RNA and serotype.

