12.2. Enrollment Period and Follow-up Period

Enrollment period: **45 months**, Follow-up period: 12 months

Initially, the study was started in October 2010 with a planned enrollment period of 24 months. However, the actual pace of enrollment was slower than expected, so the enrollment period was extended by one year in January 2012. As of August 2013, 180 patients (94.7%) have enrolled. Many patients have been unable to start the protocol treatment. Therefore, upon consultation with the research group, it was decided to extend the enrollment period, which was to conclude at the end of September 2013, by 9 months to the end of June 2014.

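### No explicit check before randomisation that every patient is suitable for hepatic arterial reservoir infusion, so infeasibility surfaces only after assignment and only in the combination arm

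*Protocol*

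**What the plan says.** - **Eligibility.** Section 4.1 has 8 inclusion criteria and section 4.2 has 23 exclusion criteria. None names hepatic arterial access, reservoir placement or contrast medium. Exclusion 21 is "Allergy to any of the study drugs". Inclusion 4 admits a patient who is "Not a candidate for complete resection by hepatectomy, local ablation therapy, or transcatheter arterial chemoembolization", without asking whether arterial infusion is still possible. The oral route is screened: exclusion 15 removes patients who cannot swallow oral medication.
- **Discretion.** Exclusion 22 covers a medical condition likely to interfere with participation. Exclusion 23 covers "Any other condition that is unstable or could jeopardize the safety of the patient or their compliance with the protocol". Both rest on the investigator's judgment.
- **Combination arm only.** Section 6.1.1 wants the catheter placed so that drug reaches the whole liver, and says "the flow should always be checked by contrast CT through the port or by DSA before starting treatment". Sorafenib may be given before infusion begins.
- **After assignment.** The site learns the assignment once eligibility is confirmed (5.2). Section 6.2 item 3 ends protocol treatment when "Hepatic arterial infusion chemotherapy becomes technically infeasible".
- **Analysis.** The full analysis set (FAS; 11.3, printed as 10.3 in the body) is limited to patients who received protocol treatment at least in part. Section 11.4 uses it for efficacy.
- **Experience so far.** Section 12.2, in explaining a 9-month extension of enrollment, reports: "Many patients have been unable to start the protocol treatment".

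**The concern.** A patient unsuitable for a reservoir can receive the full monotherapy treatment but not the full combination. Because suitability is not established for everyone before randomisation, the problem shows in one arm of an open-label trial, after the assignment is known. The plan then allows two outcomes. If the patient never starts, the FAS removes them from the combination arm, while a matching monotherapy patient stays. If the patient took sorafenib first, they stay in the combination arm without infusion. The first can make the arms non-comparable; the second pulls the hazard ratio toward 1.

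**Working it through.** **Step 1. Route of an unsuitable patient under the plan**

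| Situation | Monotherapy arm | Combination arm |
|---|---|---|
| Found unsuitable before any protocol drug | takes sorafenib, in FAS | untreated, out of FAS |
| Found unsuitable after lead-in sorafenib | takes sorafenib, in FAS | treated in part, in FAS, no infusion |

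**Step 2. The plan's own figure (12.1).** Inputs: control median 10 months, median improved by 70% (HR 1/1.7 = 0.588, stated as 0.59), 80% power, one-sided 0.05, 1:1 allocation, 112 events. Schoenfeld: d = 4(z_α + z_β)² / (ln HR)², with (ln 0.588)² = 0.2816.

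- z_α = 1.645: 4 × (1.645 + 0.842)² / 0.2816 gives 88 events.
- z_α = 1.960: 4 × (1.960 + 0.842)² / 0.2816 gives 112 events.

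So 112 matches two-sided 0.05. At the stated one-sided 0.05 with HR 0.59, 112 events give about 87% power, which is the baseline below.

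**Step 3. Dilution if all randomised patients are analysed.** Assumptions: a share f of the combination arm gets no infusion and fares as on sorafenib alone. The documents give no rate; f = 5%, 10%, 15% is illustrative (about 5, 10, 14 of 95 patients). Diluted HR = exp((1 − f) × ln 0.59). One-sided power = Φ(√d/2 × |ln HR| − 1.645).

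The 130 events come from 45 months of uniform accrual plus 12 months of follow-up (12.2), with exponential medians of 10 and 17 months. The event probabilities are 0.867 and 0.719, mean 0.793, and 164 × 0.793 = 130.

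| f | HR | Power, 112 events | Power, 130 events |
|---|---|---|---|
| 0 | 0.590 | 87% | 91% |
| 5% | 0.606 | 84% | 89% |
| 10% | 0.622 | 81% | 86% |
| 15% | 0.639 | 77% | 82% |

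A Cox simulation (95 per arm, 24 + 12 months, 3,000 runs per setting) gave HRs of 0.60, 0.62 and 0.64 for the same shares.

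**Step 4. Selective dropping from the FAS.** In the same simulation, infeasible patients were removed from the combination arm only.

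- Same prognosis as the rest (median 10 months): HR stays at 0.59, no bias.
- Worse prognosis (assumed median 6 months), f = 5%, 10%, 15%: HR 0.57, 0.56, 0.55.
- Worse prognosis and no true effect: HR 0.98, 0.96, 0.93, and one-sided type I error 7%, 8%, 11% instead of 5%.

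**The case against.** **Discretion exists.** Exclusions 22 and 23 let an investigator keep out a patient with a known contrast allergy or unsuitable anatomy, and section 8.1 collects "ECOG-PS (see Section 21.2), allergies, and concomitant diseases" before enrollment. The Enrollment Eligibility Form is not shown and may ask more. This stands: one cannot say that the protocol leaves no way to exclude such patients, or that a contrast-allergic patient is bound to pass screening. But discretion is neither uniform nor recorded as a suitability check.

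**The reported non-starters.** A reader might infer from section 12.2 that the missing criterion caused them and that they sit in the combination arm. The text gives no arm, reason or count, and both arms have a 28-day start window, so it does not support this. Nor does every infeasible patient become a non-starter, because lead-in sorafenib counts as treatment in part.

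**Contrast allergy.** A reader might take it as the main driver. Section 7.2 calls shock from iodine contrast very rare, so it is one example only.

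**Size.** The infeasibility rate is assumed. Because 112 events fit two-sided 0.05, a reader might quote power of 76%, 71% and 66%, but the protocol states one-sided 0.05. With about 130 events, one-sided power stays above 80% throughout the assumed range.

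**Design choice.** Sections 0.2 and 1 define the population by unsuitability for resection, ablation or TACE, not by suitability for infusion. Counting placement failures in an all-randomised analysis is a legitimate comparison of strategies. However, the plan does not make that comparison: its efficacy set drops patients who never start.

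**Conclusion.** The point holds as a gap in design that is cheap to close. There is no explicit, uniform suitability check before randomisation, infeasibility can stop treatment in one arm only, and the FAS turns it into either selective exclusion or dilution. Dilution is modest under assumed rates of 5% to 15%: HR about 0.61 to 0.64, and one-sided power with 112 events of 84% to 77% against 87%. Bias from selective dropping arises only if infeasible patients have a different prognosis, which the documents do not report. Analysing all randomised patients removes that bias but not the dilution; a check before randomisation reduces both. How often infeasibility occurred cannot be told from the protocol.

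**What to change.** 1. Add to section 4.1 and to the Enrollment Eligibility Form: before randomisation, the site confirms for every patient, from screening information already required (imaging and recorded allergies), that the patient is judged suitable for either assigned treatment, including arterial reservoir infusion and its contrast check. The trial team sets the clinical criteria. Screening images cannot prove whole-liver distribution, since section 6.1.1 checks flow through the port or by DSA before treatment, so this is a judgment and some later failures will remain.
2. Report non-starters, and combination patients who received no infusion, by arm and reason.
3. Analyse OS in all randomised patients.

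The cost is one eligibility line and one box on the form, with no new procedure. Recruitment may slow slightly, and the population must be described as suitable for either treatment. The revision history ends in June 2015, after the planned close of enrollment in June 2014. If accrual has closed, only items 2 and 3 can still be done, and they should be.

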5. ENROLLMENT

5.1. Enrollment and Randomization Procedures

After confirmation that a prospective participant meets all of the inclusion criteria and none of the exclusion criteria, the required sections of the Enrollment Eligibility Form will be completed and the form faxed to the data center.

Contact information and hours for patient enrollment office

Data Center Japan Clinical Research Support Unit (J-CRSU)
[name]
[name]

[contact]

[contact]

Hours: Weekdays from 10:00 AM to 5:00 PM (excluding holidays and New Year's holiday period)

Direct correspondence about criteria for patient selection to:

Study coordinator [name]
Department of Gastroenterology and Hepatology, Kindai University
Faculty of Medicine

[contact]
[contact]
e-mail: [contact]

5.2. Notes Regarding Enrollment

- 1) No patients will be enrolled after the start of the protocol treatment, with no exceptions
- 2) Patients will be enrolled by faxing the Enrollment Eligibility Form to the data center
- 3) If the data center is unable to fully review information on the Enrollment Eligibility Form, the patient will not be enrolled until they are confirmed to meet all requirements
- 4) Once the data center confirms eligibility, patients will be issued an enrollment number and informed of their assigned treatment
- 5) The data center will fax to the institution a Confirmation of Enrollment and Notification of Assigned Treatment form with the patient's enrollment number
- 6) Enrollment will be concluded with the sending of this form. The Confirmation of Enrollment and Notification of Assigned Treatment forms shall be retained by each institution.
- 7) Except for patients who withdraw their consent (including patients who decline use of their information for research purposes), patients who have been enrolled cannot be unenrolled (i.e., removed from the database). If the same patient is enrolled multiple times, the information from the first enrollment (enrollment number and treatment group) will always be used.
- 8) Erroneous enrollments and multiple enrollments should be reported to the data center soon after they are noticed

5.3. Randomization and Stratification Factors

Patients will be randomized into the low-dose FP plus sorafenib group (combination therapy) or the sorafenib group (monotherapy) in a 1:1 ratio. Group assignments will be made using a computer program.

The following items will be used as stratification factors for randomization with the minimization method.

- (1) Institution
- (2) Macroscopic vascular invasion (MVI) (Vp0, Vp1-3, Vp4)
- (3) Presence/absence of extrahepatic spread (EHS)

6. TREATMENT PLANS AND CRITERIA FOR ADJUSTING TREATMENT

6.1. Protocol Treatments

6.1.1. Low-dose FP and sorafenib group (combination therapy group) (Table 1)

This study will use the following doses demonstrated as safe in a phase I/II study of sorafenib and low-dose cisplatin/fluorouracil hepatic arterial infusion chemotherapy for advanced hepatocellular carcinoma. Cisplatin will be administered at a dose of 20 mg/m² on day 1 (within 30 days), and fluorouracil will be administered at a dose of 330 mg/m²/day by hepatic infusion using a reservoir for 5 days from day 1 through day 5 (continuous infusion over 24 h), followed by 2 days off. This sequence will be repeated for 2 weeks, followed by 2 weeks off. Sorafenib will be administered continuously at a dose of 400 mg twice daily for 28 days from day 1 to day 28. This 4-week period constitutes one cycle.

The first cycle of treatment will be started within 28 days of randomization. Treatment with sorafenib before hepatic arterial infusion chemotherapy will be allowed. However, patients must be off sorafenib for 2 days before and 7 days after reservoir placement. The next cycle of treatment will be started within 14 days. Sorafenib will be continued until the start of the next cycle. This combination therapy will be continued until discontinuation of the protocol treatment.

If an adverse event is observed, treatment will be interrupted or the dose will be reduced as appropriate in accordance with **6.3.2. Criteria for adjusting the sorafenib dose (dose interruption and reduction)** and **Section 6.3.3. Criteria for Hepatic Arterial Infusion Chemotherapy (Low-dose FP) Dose Adjustment (Dose Interruption and Reduction)**. After the protocol treatment is discontinued, appropriate treatment as described in **Section 6.5 Post-trial Treatment** will be instituted.

The arterial catheter should be placed in a manner that allows for proper drug distribution throughout the liver, and the flow should always be checked by contrast CT through the port or by DSA before starting treatment.

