0.5. Treatments

0.5.1. Combination therapy with low-dose FP and sorafenib

Low-dose cisplatin will be administered on day 1, and fluorouracil will be administered by hepatic infusion using a reservoir for 5 days from day 1 through day 5, followed by 2 days off. This sequence will be repeated for 2 weeks, followed by 2 weeks off. Sorafenib will be administered continuously at a dose of 400 mg twice daily for 28 days from day 1 to day 28. This 4-week period constitutes one cycle, and cycles will be repeated until discontinuation of the protocol treatment. The first cycle of treatment will be started within 28 days of randomization. Earlier treatment with sorafenib will be allowed. However, patients must be off sorafenib for 2 days before and 7 days after reservoir placement. The next cycle of treatment will be started within 14 days. However, sorafenib will be continued during that time. This combination therapy will be repeated until progressive disease (PD) according to the modified RECIST criteria is documented [1]. (However, observation of a new intrahepatic lesion will not be considered PD.)

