8.2. Tests and Evaluations during the Study Period

8.2.1. Parameters evaluated during the first cycle

Data on the following parameters will be collected each week during the first cycle.

- 1) Signs and symptoms* and blood pressure
- 2) Hematology parameters: Hemoglobin, white blood cell count, neutrophil count, red blood cell count, platelet count

3) Blood biochemistry: AST, ALT, total bilirubin, direct bilirubin, ALP, γ -GTP, albumin, creatinine, Na, K, Cl, amylase, lipase, blood glucose

*: Signs and symptoms will be recorded using terms from the Japanese translation of CTCAE v4.0.

4) Coagulation: PT (INR)

5) Adherence to study treatment

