9. DATA COLLECTION

9.1. Types of Case Report Form (CRF) and Submission Deadlines

The types of case report forms used in this study and their submission deadlines are as follows.

- 1) Enrollment Eligibility Form: Fax to data center at enrollment
- 2) Patient Characteristics Report: Fax to data center within 2 weeks before the start of the study
- 3) Progress Report (each cycle): Fax to data center within 1 week after eligibility to start next cycle is confirmed
- 4) SAE Report (Expedited Primary Report): Fax to **study coordinator** within 72 hours of SAE onset
- 5) SAE Report (Expedited Secondary Report): Fax to **study coordinator** within 7 days of learning of the event
- 6) Adverse Event Report (Normal Report): Fax to **study coordinator** within 15 days of learning of the event
- 7) Treatment Response Report: Fax to data center within 4 weeks after the end of the protocol treatment
- 8) Treatment Completion Report: Fax to data center within 4 weeks after the end of the protocol treatment
- 9) Follow-up Form: Fax to data center within 2 weeks after receiving a request*
- 10) Treatment Suspension Report: Fax to the study chair when considering discontinuation for a patient who does not clearly meet the specified criteria for discontinuation of the protocol treatment

*Will be requested every 4 months following the monitoring schedule of the data center after the end of the study treatment.

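### Sorafenib taken before cycle 1 in the combination arm falls outside every scheduled assessment, while the monotherapy arm's first exposure is checked weekly

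*Protocol*

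**What the plan says.** **Permission.** The synopsis (Section 0.5.1) states "Earlier treatment with sorafenib will be allowed" for the combination arm, and Section 6.1.1 repeats it as "Treatment with sorafenib before hepatic arterial infusion chemotherapy will be allowed". The only conditions are the interruption around the procedure, "patients must be off sorafenib for 2 days before and 7 days after reservoir placement", and the general limit "The first cycle of treatment will be started within 28 days of randomization". Section 6.1.2 has no matching provision for monotherapy.

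**What a cycle is.** Section 6.1.1 gives "Cisplatin will be administered at a dose of 20 mg/m² on day 1" and "Sorafenib will be administered continuously at a dose of 400 mg twice daily for 28 days from day 1 to day 28". Table 1 draws all three drugs starting on the same day 1.

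**Assessments.** Section 8.1 sets the pre-enrollment tests within 4 weeks before enrollment. Section 8.2.1 then says "Data on the following parameters will be collected each week during the first cycle". Section 8.2.2 places later checks just before each cycle from the second onward. Table 11 moves from the pre-treatment column directly to week 1 of cycle 1.

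**Forms.** Section 9.1 lists "Progress Report (each cycle): Fax to data center within 1 week after eligibility to start next cycle is confirmed".

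**Use of the data.** Section 11.4 puts randomized patients in the safety evaluation, and Section 11.6.2 tabulates adverse events by group and grade. Sections 11.1, 11.5 and 12.3 plan analyses by average sorafenib dose, and the last two also by total dose.

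**The concern.** In the monotherapy arm the first sorafenib dose is cycle 1 day 1, so early exposure falls inside the weekly schedule. A combination patient who uses the lead-in has the first exposure before that schedule opens. The difference comes from the protocol itself and exists in one arm only.

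It matters most for changes found only by measuring. The package-insert excerpt in Section 7.1.1 lists raised lipase in 58.6%, raised amylase in 40.7% and hypertension in 27.6% of 145 patients. If one arm is tested weekly in its first weeks on the drug and the other is not, these changes can be detected unequally, and the by-group safety table would carry that difference. Doses taken or missed in the lead-in also belong to a patient's average and total sorafenib dose, yet no scheduled adherence check covers them.

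**Working it through.** The protocol states no figure for this period, so there is none to reproduce. The check is a comparison of schedules plus a day count.

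**Step 1: where the lead-in falls.** Section 5.2 bars enrollment after protocol treatment has begun, so lead-in sorafenib given as protocol treatment comes after enrollment. Day 1 of a combination cycle carries cisplatin and fluorouracil, so sorafenib before infusion comes before cycle 1. The lead-in lies between the two.

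**Step 2: what is scheduled in that interval.**

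| Source | Timing | Covers the lead-in? |
|---|---|---|
| Section 8.1 | Within 4 weeks before enrollment | No, earlier |
| Section 8.2.1 | Weekly in cycle 1 | No, later |
| Section 8.2.2 | Before cycle 2 onward | No, later |
| Section 6.3.1 laboratory criteria | Before the next cycle | No, does not address cycle 1 |
| Section 9.1 Progress Report | Per cycle | Not stated |

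The gap appears in the prose of Sections 8.1 to 8.2.2, so it does not depend on the layout of Table 11.

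**Step 3: how long it can last.** Inputs from Section 6.1.1: window W = 28 days, 2 sorafenib-free days before placement and 7 after. The text does not say whether the placement day itself is also sorafenib-free, so both counts are given.

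- Sorafenib started before placement: 28 − 2 − 7 = 19 days, or 18 if the placement day is also off.
- Reservoir placed at once, sorafenib started 7 days later: 28 − 7 = 21 days, or 20 if the placement day is also off.
- No placement inside the window (an assumption): 28 days.

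With placement inside the window, the maximum is therefore 18 to 21 days.

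**Step 4: comparison with control.** 18/7 = 2.6 and 21/7 = 3.0, so the same length of first exposure in the monotherapy arm contains 2 to 3 complete weekly intervals. The full first 28 days contain 28/7 = 4 weekly checks. The lead-in contains none.

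**Step 5: age of the last scheduled tests.** If enrollment and randomization fall on the same day, the pre-enrollment tests can be 28 + 28 = 56 days old at cycle 1 day 1. The same limit applies to monotherapy, but those patients have taken no study sorafenib by then.

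**The case against.** **Adverse events are not tied to cycles.** Section 7.4 requires investigators to watch for adverse events over the whole study and to record all of them on case report forms. Section 7 counts abnormal laboratory values as adverse events. Expedited and regular reports are driven by events, and the dose-adjustment rules of Section 6.3.2 are not limited to numbered cycles. This stands. A reader might infer that lead-in toxicity goes unrecorded, and the protocol does not support that. Symptomatic events should be captured. What remains open is the silent change that nobody is scheduled to look for.

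**Bleeding around the procedure.** A reader might see the period around reservoir placement as unmonitored, given the warning in Section 7.3 that sorafenib may worsen hemorrhage. The same section promises careful monitoring, and Section 6.1.1 requires sorafenib to be stopped around placement. The fair statement is that no scheduled visit puts that promise into practice.

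**Perhaps the first sorafenib dose opens cycle 1.** The weekly checks would then cover the lead-in. The common day 1 in Section 6.1.1 and Table 1 weighs against this reading. If it is intended, the text needs to say so.

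**The forms are not shown.** The cycle 1 Progress Report may ask about earlier sorafenib. Section 9.1 does not say so, but it does not exclude it either.

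**Size and direction.** A reader might multiply 18 days by 800 mg per day to get 14.4 g of unchecked exposure, but no lead-in dose is given; 400 mg twice daily is only the one starting dose the protocol states. A reader might also infer that the average-dose analysis is biased toward the combination. That analysis is planned as a subgroup or stratified analysis, and leaving out the lead-in would drop both dosing days and compulsory off days, so no direction follows. The primary endpoint, survival from randomization, is not affected.

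**Conclusion.** The point holds as a gap in scheduled assessment, confined to one arm and to patients who use the lead-in. As written, up to about 18 to 21 days of first sorafenib exposure can pass with no scheduled check, against 2 to 3 weekly checks over the same exposure in the control arm. The consequence is possible under-detection of early silent laboratory and blood pressure changes in the combination arm, and no scheduled capture of lead-in dosing for the dose analyses.

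This rests on reading cycle 1 day 1 as the first infusion day, and on reservoir placement falling inside the 28-day window. The protocol does not state uptake, so any number from 0 to all 95 planned combination patients could be affected. The documents support a risk of unequal detection. They do not show that a bias of known size or direction has been introduced.

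**What to change.** Reconcile Sections 0.5.1, 6.1.1, 8.2.1 and 9.1 and Tables 1 and 11 on two questions: what event starts cycle 1, and where the assessment schedule begins. The wording should anchor the following to the first dose of any study drug, in both arms:

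- the scheduled assessments in Section 8.2.1 and Table 11, with a place in the table for the period before cycle 1;
- case report form capture of sorafenib dosing, interruptions and adverse events, for example by stating that the cycle 1 Progress Report reaches back to that dose;
- the start of the period used for the safety tabulation and for average and total sorafenib dose.

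The same clarification should settle what counts as the start of treatment for the imaging schedule in Section 8.5. No dose or treatment rule needs to change.

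The cost is some wording, one addition to Table 11 and a few additional routine checks in patients who use the lead-in.
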